6 STUDY INTERVENTION

6.1 STUDY INTERVENTION(S) ADMINISTRATION

6.1.1 STUDY INTERVENTION DESCRIPTION

The mobile application, developed at the University of Michigan, includes two JITAIs that are turned on or off based on the randomization assignment for the clinical trial. The clinical worsening intervention promotes self-monitoring and self-management with a health status indicator that is linked to adaptive, personalized and contextual push notifications to promote a behavioral change (see figure 2). The dietary sodium intervention facilitates lower sodium choices at home, restaurants, and grocery stores using tailored and contextual push notifications.

Both JITAIs use NumberEight, an internet-based service, that use sensors (Wi-Fi, Bluetooth, accelerometer, gyroscope, magnetometer, GPS) on the participant's device to predict their location. User's identifying information is anonymized in NumberEight. The mobile sensor data and NumberEight profiles are not attached to the personalized identifiers (e.g. phone number, email). Data are stored as long as the user is using NumberEight. Study staff will not have access to participants' location during the study period.

Clinical worsening intervention: The intervention adapts to the participant's reported symptoms and provides feedback with a global health status indicator (HSI). The mobile application includes 8 questions which are completed by all (see table 1). After the questions are answered, participants

randomized to the clinical worsening intervention arm will be shown the HSI screen. Access to the HSI screen is restricted to participants in the clinical worsening intervention arms. The HSI screen presents a graphic (figure 2). The HIS graphic is a speedometer-like pictograph that goes from green (good health status) to yellow (fair health status) to red (poor health status). The movement from green to yellow to red is based on the answers to each daily questionnaire. The health status indicator includes text explaining the green, yellow or red status and what they can do for self-management. Additionally, users will receive two push notifications per day in the yellow and three push notifications per day in the red until they are back in the green. The notifications will link to in-app educational content, if appropriate for the notification.

Question score	0	1	2	3	4
Sense of fullness during a meal earlier than usual	Never	Rarely	Sometimes	Most of the time	Always

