When a participant is randomized to both interventions, the user can receive several messages throughout the day, overburdening the participant and causing user fatigue. In order to reduce message burden, we maximize the number of messages a user can receive in one day to three messages for both interventions. We also authenticate that both interventions are presented. For example, if a user receives a morning clinical worsening intervention message and receives two dietary sodium intervention messages, they will not receive another message. The following day, the app prioritizes the clinical worsening intervention to present at least two messages because of the previous day. Ultimately, this averages both interventions to deliver 1.5 messages per day over a week.

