10.4 PROTOCOL AMENDMENT HISTORY

Version	Date	Description of Change	Brief Rationale
1.1	2020.12.17	Section 1.3: Moved the timing of the HADS and nutritional assessments from day of discharge to screening/enrollment.	This will streamline the workflow. Coordinators will be present to answer participants' questions and ensure data collection is completed. This will also decrease the amount of activities the participant needs to complete immediately upon discharge.
		Section 8.2 Added the HRQOL and nutritional assessments to the list of items at the screening/baseline visit.	For internal consistency within the protocol to match the change described above. Section 8.2 now matches the schedule of activities.
1.2	2021.04.09	Added language to describe the smartphone inclusion criteria more clearly (bolded text is new): A smartphone with a compatible Apple or Android operating system installed and able to download and use ManageHF including accepting all permissions	To ensure the app works as intended, the smartphone must run a compatible operating system and all permissions must be accepted.
1.2	2021.12.03		The study workflow has been updated to reflect the changes included in this amendment.
1.3	2021.12.03	Screening, recruitment, enrollment, and the baseline	Recruitment and enrollment have been slower than

		visit can now occur up to 7 days post-discharge. The visit windows for weeks 6 & 12 have been extended to +/-10 days.	anticipated. The sites have indicated they are experiencing challenges approaching participants before discharge. It is expected that extending the enrollment and baseline visits to up to 7 days post-discharge will improve enrollment by giving the participants and coordinators additional time to complete all enrollment activities.
		The 1-question NHYA survey is not required for randomization	Due to low survey completion at weeks 6 & 12, we are extending the visit windows to give participants more time to complete the survey and give the coordinators more time to follow up.
		Process for randomizing participants who are rehospitalized has been spelled out.	This one question survey is not a primary outcome measure and we do not want to lose participants due to 1 missing question.
			By allowing enrollment to occur after discharge, there is a higher likelihood a participant could be rehospitalized prior to randomization.

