8.3.7	2021.12.03	Revised text (bolded text is added): SAEs are reportable from the time of discharge or consent (based on hospitalization status) until a subject	The clarifying language is necessary to describe the timeframe for collecting SAEs based on hospitalization status at enrollment (inpatient vs outpatient).
10.1.9.1	2021.12.03	Added text: Due to the length of the FFQ, paper copies may be available for participants who prefer to complete a paper and pencil version.	Due to the length of the FFQ, the sites have indicated some of their participants would prefer to complete the survey via paper instead of electronically.
10.1.3	2021.12.03	activate the devices, the University of Michigan and	Providing Withings with the participant's email address will allow the participant to receive a shipping confirmation email with tracking information.
10.3	2021.12.03	Added: AESI to the abbreviation table.	Added for internal consistency of the document.
1.2, 5.1, 5.2	2022.04.18	Update inclusion and exclusion criteria	Due to lower than expected recruitment, the inclusion and exclusion criteria have been revised to include a broader pool of patients with heart failure.
5.4	2022.04.18	Added compensation with timing and dollar amount.	Participant incentives have been added to improve

	Added texting as a participant contact method.	participant recruitment and retention The DSMB recommended adding texting as participant contact method to improve participant retention.

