8.3 Primary Endpoint Definition

The primary outcome is a hierarchical composite of time to all-cause death, time to first HF readmission, and change from baseline to week 12 in MLHFQ using the win ratio.

Death (from any cause) occurring during the study period will be reported by each site. We do not expect an intervention effect on death but are including the event because of its importance using this methodology.

Readmission is defined as admission to an inpatient unit or stay in an emergency department following discharge after the index hospitalization that results in at least a 24-hour stay.³⁰ Only admissions associated with events that occur on an emergency or unplanned basis will be considered as potential endpoints and then adjudicated. A HF readmission must have clinical manifestation of new dyspnea, orthopnea, paroxysmal nocturnal dyspnea, edema, pulmonary basilar rales/crackles, jugular venous distension, renal hypoperfusion with no other apparent cause or radiological evidence of acute HF and additional increased treatment with either intravenous HF medications (diuretics, inotropes, vasodilators) or mechanical or surgical intervention specifically directed at the treatment of HF. Only readmissions during the study period will be assessed.

The MLHFQ tool consists of 21 questions regarding patients' perception of the effects of HF on their daily lives.²⁹ The questions produce a total score of 0 to 105, with a higher score indicating poorer HRQOL. The MLHFQ will be collected at baseline, 6 and 12 weeks. A score change of 5 or more is considered a clinically significant difference for the hierarchical composite endpoint.

Following the unmatched pairs win ratio method of Finkelstein and Schoenfeld,³⁴⁻³⁶ each participant receiving intervention will be compared to each participant not receiving intervention, resulting in $N_i \times N_{ni}$ pairwise comparisons, where N_i is the sample size for the intervention arm, and N_{ni} is the sample size for the non-intervention arm. For each comparison, "winners" will be determined according to the table below, starting with scenario 1.

Scenario	Time to all-cause death	Time to HF readmission	Change in MLHFQ	Win/loss
1	Low			Loss
	High			Win
2	Tie or both alive	Low		Loss
		High		Win
3	Tie or both alive	Tie or both not hospitalized	Comparator	Loss
			12-week change ≥ 5 points better than comparator	Win
4	Tie or both alive	Tie or both not hospitalized	Comparator	Tied

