8.6 Missing Data

Assessment of the extent of missing data and its mechanism will be explored for the primary endpoints using the ITT analysis set. Graphical and numerical descriptive methods will be used to summarize the primary outcome over time, by intervention group and overall. We will begin by assuming missing at random and employ multiple imputation methods to handle missing data at the discretion of the study statistician.

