9.4 Demographic and Baseline Variables

All the following demographic and baseline variables will be summarized overall and by treatment group.

Demographic characteristics will be summarized: age (years); age (18-35, 36-50, 51-65, 66 to 80, >80 years, missing); sex at birth (male, female, not reported); ethnicity (Hispanic or Latino, not Hispanic or Latino, unknown or not reported); race (white, black or African American, Asian, American Indian or Alaskan Native, Native Hawaiian or Other Pacific Islander, Multi Race, Unknown or Not Reported).

Baseline characteristics will be summarized: heart failure type (reduced ejection fraction, preserved ejection fraction); NYHA (category 1, category 2, category 3, category 4, missing); baseline MLHFQ score; baseline sodium screener (mg/dL); heart rate; systolic blood pressure.

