10.3 Primary Analysis of Secondary Endpoints

Secondary endpoints will be summarized overall and by treatment groups: time to all-cause mortality, time to first heart failure readmission, and change in MLHFQ over 12 weeks.

Simple Cox proportional hazard models will be used to assess time to all-cause mortality and time to first heart failure readmission as a function of treatment group assignments. Hazard ratios and 95% confidence intervals will be reported. Kaplan-Meier curves will be used to visually assess time to all-cause mortality and time to first heart failure readmission by treatment group assignments.

Simple linear regression models will be used to assess the outcome of change in MLHFQ over 12 weeks. Beta coefficients and 95% confidence intervals will be reported. Estimated marginal means for each treatment group will be computed with 95% confidence intervals. The outcome of change in MLHFQ over 12 weeks will be visually assessed with side-by-side box plots (by each treatment group status).

11 Safety Analyses

The number and proportion of participants with SAEs, (including segregation of those involving deaths), treatment-emergent AEs, and discontinuation of study intervention due to AEs will be presented, overall, and by randomization group (both intervention, diet intervention only, clinical worsening intervention only, neither intervention). These presentations will be descriptive, with no formal inferential methods used. The JITAs are not expected to pose a great risk to participant safety. Thus, no specific rules for halting study enrollment or study interventions for safety are specified.

In accordance with clinicaltrial.gov reporting requirements, the following tables are required and will be provided:

- All-Cause Mortality: A table of all anticipated and unanticipated deaths due to any cause, with the number and frequency of such events by arm or comparison group of the clinical study.
- Serious Adverse Events: A table of all anticipated and unanticipated serious adverse events, grouped by organ system, with the number and frequency of such events by arm or comparison group of the clinical study. (See Adverse Events definition below).
- Other (Not Including Serious) Adverse Events: A table of anticipated events of special interest (not included in the serious adverse event table) with the number and frequency of such events by arm or comparison group of the clinical study.

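### SAP 10.3 leaves baseline MLHFQ out of the model for 12-week MLHFQ change, which costs precision (about 14% of residual variance at pilot values) but does not invalidate the analysis

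*SAP*

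**What the plan says.** SAP 10.3: "Simple linear regression models will be used to assess the outcome of change in MLHFQ over 12 weeks". The outputs are regression coefficients, confidence intervals, marginal means and box plots by treatment group. No covariate is named.

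SAP 8.3: "The MLHFQ will be collected at baseline, 6 and 12 weeks". Protocol 6.1.2 and the second footnote to the schedule of activities (Protocol 1.3, SAP 6.4) put the baseline questionnaire before randomization. SAP 9.4 lists "baseline MLHFQ score" among the variables to be summarized, but no model in the SAP uses it as a covariate.

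Protocol 9.3.2 had planned longitudinal models for MLHFQ and multivariable models adjusted for site, sex, race and HF type. SAP 14 withdraws the adjustment for those factors because the study ended early. Baseline MLHFQ is not one of them.

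On missing data, SAP 8.6 is worded for the primary endpoints. It starts from missing at random and would "employ multiple imputation methods to handle missing data at the discretion of the study statistician". SAP 10.3 gives no rule of its own.

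**The concern.** Baseline MLHFQ enters only by subtraction, which fixes its coefficient at 1. If week-12 scores rise by less than one point per point of baseline, subtraction over-corrects and leaves avoidable noise in the outcome. A covariate measured before randomization, and held for every correctly randomized participant, would remove that noise for one degree of freedom. The trial was stopped for insufficient enrollment, so wide intervals are to be expected. What is at stake is the width of the interval for one secondary endpoint.

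**Working it through.** The documents give no SD, correlation or power for this endpoint, so there is no stated figure to reproduce. The only usable data are the web-application pilot in Protocol 2.2.

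**Inputs.** n = 24; MLHFQ 55.7 ± 4.6 before and 42.6 ± 5.1 after; p = 0.0078. The ± values must be standard errors. Read as SDs, the standard error of the difference could be at most (4.6 + 5.1)/√24 = 1.98, giving t of at least 13.1/1.98 = 6.6 and p below 0.000001. A paired t-test is assumed.

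**SDs and correlation**
- t on 23 df for p = 0.0078 is 2.915. SE of change = 13.1/2.915 = 4.49. SD of change = 4.49 × √24 = 22.0.
- SD before = 4.6 × √24 = 22.5. SD after = 5.1 × √24 = 25.0.
- r = (22.5² + 25.0² − 22.0²)/(2 × 22.5 × 25.0) = 0.575.
- 95% interval: tanh(atanh(0.575) ± 1.96/√21) = 0.22 to 0.79.

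**Precision**

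Variance ratio, adjusted to unadjusted = (1 − r²)SDpost² / (SDpre² + SDpost² − 2·r·SDpre·SDpost). The excess variance of the unadjusted analysis is (SDpre − r·SDpost)², which is never negative. It is zero only at r = SDpre/SDpost, here 22.5/25.0 = 0.90.

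| r | Variance ratio | Cut |
|---|---|---|
| 0.22 | 0.67 | 33% |
| 0.575 | 0.862 | 14% |
| 0.79 | 0.97 | 3% |

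With equal SDs the ratio is (1 + r)/2, so the cut is 35% at r = 0.3 and 15% at r = 0.7. At the pilot value the unadjusted model needs 1/0.862 = 1.16 times as many participants for the same precision.

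The lost degree of freedom is charged by the factor 1 + 1/(N − 4). Half-width is t × 22.0 × √(4/N), times the square root of the net ratio when adjusted. Both N are assumed.

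| N | Net ratio | Unadjusted half-width | Adjusted half-width |
|---|---|---|---|
| 100 | 0.862 × 1.010 = 0.871 | 8.74 | 8.16 |
| 60 | 0.862 × 1.018 = 0.878 | 11.38 | 10.66 |

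At r = 0.79 the net gain is only 2% and 1% of variance.

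**Bias**

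Let δx and δy be the shifts in mean baseline and mean week-12 score among completers of one arm relative to the other. The slope of week 12 on baseline is 0.575 × 25.0/22.5, or 0.637 with unrounded SDs. The unadjusted bias is then δy − δx, and the adjusted bias about δy − 0.637δx.

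- *Missingness driven by baseline alone, in one arm.* δy = 0.637δx, so the adjusted bias vanishes and the unadjusted bias is −0.363δx.
- *Missingness driven by mid-trial symptoms with the same correlation c to both scores.* With δz the shift in symptoms in SD units, δx = 22.5cδz and δy = 25.0cδz. The unadjusted bias is 2.5cδz; the adjusted bias is (25.0 − 0.637 × 22.5)cδz = 10.7cδz, about four times as large.

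Simulation agrees (N = 100, no true effect, dependence in one arm, log odds ratio 1 per SD; bias in points):

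| Missingness depends on | Missing | Unadjusted | Adjusted |
|---|---|---|---|
| Baseline | 20% | 1.4 | within 0.1 of zero |
| Baseline | 30% | 2.0 | within 0.1 of zero |
| Mid-trial symptoms (various assumed correlations) | 20% to 30% | +0.3 to −1.3 | −0.8 to −2.6 |
| Week-12 score | 30% | −3.1 | −4.3 |

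With 30% missing completely at random, or with the same dependence on baseline in both arms, neither estimate was biased beyond simulation error. In the symptom-driven settings the sampling variance ratio stayed at 0.86 to 0.90, and root mean squared error was lower or about equal with adjustment.

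**The case against.** The strongest reply is that unadjusted change is a legitimate analysis, matches the endpoint as defined, and belongs to an openly simplified plan for a stopped trial. All of that stands. The pilot is also thin: 24 users of an earlier web application, with no control group. If the true SDs were 20 and 25 with r = 0.79, the variance ratio would be 1.00 and the gain nil. That stands too, and is why a range is given. It does not explain omitting the covariate, since the expected cost is one degree of freedom.

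A reader might go further and infer that the unadjusted model is biased by differential dropout and that the covariate would cure it. The ingredients seem to be there. The amendment history records: "Due to low survey completion at weeks 6 & 12, we are extending the visit windows". In the clinical worsening arms, "users will receive two push notifications per day in the yellow and three push notifications per day in the red". Protocol 6.1.2 says that with both interventions "the user can receive several messages throughout the day, overburdening the participant and causing user fatigue".

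The documents do not support that inference:
- Low completion is not reported by arm or by baseline score. It predates the wider windows, texting and payments, and no later rate is given.
- The notifications follow the daily questionnaire answers, that is, current symptoms rather than baseline MLHFQ. Under that mechanism the covariate can increase bias, as shown above.
- The fatigue remark concerns participants assigned to both interventions, and the protocol caps their messages for that reason.
- The factorial design balances the clinical worsening intervention across the dietary groups, so its notifications give no ready reason for differential loss in the dietary comparison.
- Imputation under SAP 8.6 using baseline and arm would largely remove bias from baseline-dependent missingness, although the SAP does not commit to it here.

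**Conclusion.** The point holds as one of precision. SAP 10.3 omits an available pre-randomization covariate, at an expected cost of about 14% of residual variance, with a plausible range from near zero to about a third. This rests on the pilot summary, the standard-error reading, a paired t-test and the assumed N. Adjustment removes bias only where missingness depends on baseline and arm alone, which the documents do not show, so no general reduction in bias is claimed.

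The consequence is modest. The endpoint is secondary, Protocol 9.3.1 calls such analyses hypothesis-generating, and the win-ratio test is unaffected. With or without the covariate, the half-width at either assumed N exceeds the 5 points in SAP 8.3. This is an improvement to consider, not an error that undermines the plan. The replacement of the protocol's longitudinal model is covered in general terms by SAP 14 and is not part of the point.

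**What to change.** In SAP 10.3, write: *Change in MLHFQ at week 12 will be analysed by linear regression on the intervention with baseline MLHFQ as a covariate; the adjusted difference, 95% CI and adjusted marginal means will be reported for each intervention. The number with a week-12 score and their mean baseline MLHFQ will be reported by group.*

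The second sentence lets a reader see whether completers differ at baseline, so that the missing-data question can be judged from data. The change is best fixed before results by group are seen.

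The cost is one covariate, one descriptive row and one degree of freedom (about 1% of variance at N = 100 and 2% at N = 60, already included above). All the data are collected, and no stratification factor is restored. The report should say that adjustment does not protect against week-12 scores missing because of later symptoms or the week-12 state itself.

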We developed a mobile application that can effortlessly assist in self-monitoring, ultimately driving self-management in HF. Version 1 of the application provided patients a health status indicator (HSI) using standard stop light color concept (green, yellow, red) and a message explaining the meaning of the HSI. A deterministic algorithm, based on a daily survey and the change in patient weight compared to dry weight, produces the number for the HSI. See figure 2 for a depiction of the HSI page. We studied this intervention in a randomized clinical trial, which was Aim 1 of an R21 funded by the National Institute on

Aging. We hypothesized that the HSI would accomplish enhanced self-management and improve HRQOL. HF patients at hospital discharge were randomized to the App or usual care (No App) in a 1:1 fashion and followed for 12 weeks. The MLHFQ was collected at baseline, 6 weeks and 12 weeks and HF readmissions were collected over the 12 weeks. Eighty-three patients were enrolled and completed all baseline assessments. Baseline characteristics were similar between groups, except HF type. The average age is 60.2 and 62 years in the App and No App arms, respectively. Most patients were NYHA class III, 58% had ischemic heart disease as the origin of HF, 57% had atrial fibrillation and 35% were female. The App group had a reduced MLHFQ at 6 weeks (p=0.039) but not at 12 weeks (p=0.778) compared to control. The time to first HF readmission was not statistically different between the two groups, but in favor of the App group (App 26.2% vs. No App 19.3%, HR 0.89, 95% CI 0.39-2.02, p=0.781).

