4.3 JUSTIFICATION FOR DOSE

The "doses" or intensity of the interventions in this study have been investigated in preliminary work in focus groups, surveys, and clinical trials. In general, patients felt that the number of push notifications was appropriate for the dietary sodium intervention, so we based the max number of push notifications

per day for both interventions off that premise. When a participant is randomized to both interventions, the user can receive several messages throughout the day, overburdening the participant and causing user fatigue. In order to reduce message burden, we maximize the number of messages a user can receive in one day for both interventions.

HF patients are at greatest risk for hospital readmission and death for 7-weeks post-discharge and then the risk plateaus.²⁵ To account for the increased risk for 7 weeks post-hospitalization, participants will be followed for 12 weeks to capture data both during the highest risk phase and as patients enter a lower risk period.

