Within each pairing, the participant with the longest survival time is counted as the "winner" of that pairing. The win ratio is the number winners divided by the number of losers associated with the intervention. The estimate of the win ratio will be calculated, and its 95% confidence interval will be calculated using bootstrap methods. The test for intervention effect is a nonparametric rank sum test. In the event there is more than a 10% loss-to-follow-up, sensitivity analyses based on multiple imputation of the primary outcome will be conducted. However, if some lost or withdrawn participants were readmitted to hospital, a determination may still be possible for the win ratio statistic.

For secondary endpoints, individual components of the composite outcome will be examined, using survival methods for time-to-event outcomes, and linear mixed effects models or piecewise linear regression for longitudinal continuous outcomes (e.g., MLHFQ). The proportion of participants experiencing 30-day readmissions will be analyzed using logistic regression. Number and percent of days alive and out of hospital (DAOH) will be analyzed using linear regression.³⁹ Repeated measures proportional odds logistic regression⁴⁰ will be used to compare NYHA classifications (ordinal measurements).²⁷ If the proportionality assumption does not hold, the outcome will be dichotomized and a generalized linear mixed model will be used.

For the primary analysis, the following stratification factors will be explored: site, sex, race, and HF type (HFpEF versus HFrEF). For the secondary analyses, the same stratification factors will be explored, and multivariable models will be fit adjusted for the same variables. A subgroup analysis will be conducted to examine intervention effects by cognition and depression status. In addition, we will explore whether there is a signal for an interaction effect for the use of both mobile applications.

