5.2 Endpoints

5.2.1 Primary Endpoint

1. The hierarchical composite of time to death from any cause, time to first HF readmission, and change from baseline to week 12 in quality of life as measured by the Minnesota Living with Heart Failure Questionnaire (MLHFQ).

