9.2 Derived variables

Derived variables include:

1. Treatment groups
 1. Dietary intervention (Yes/No)
 2. Clinical Worsening (Yes/No)
2. Win Ratio - The primary outcome is a hierarchical composite of time to all-cause death, time to first HF readmission, and change from baseline to week 12 in MLHFQ using the win ratio.
3. Change in MLHFQ over 12 weeks.

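### SAP 10.3 replaces the protocol's longitudinal MLHFQ model with a single week-12 change score, so no treatment effect is estimated at or using week 6, and SAP 14 does not list the switch

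*SAP*

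**What the plan says.** - **Collection.** SAP 8.3: "The MLHFQ will be collected at baseline, 6 and 12 weeks".
- **Endpoint.** The third tier of the primary composite (SAP 5.2.1) is the "change from baseline to week 12 in quality of life as measured by the Minnesota Living with Heart Failure Questionnaire (MLHFQ"). Protocol 8.1 defines the MLHFQ secondary outcome over the same interval. The only MLHFQ variable derived in SAP 9.2 is "Change in MLHFQ over 12 weeks".
- **Protocol model.** Protocol 9.3.2 names "linear mixed effects models or piecewise linear regression for longitudinal continuous outcomes (e.g., MLHFQ").
- **SAP model.** SAP 10.3: "Simple linear regression models will be used to assess the outcome of change in MLHFQ over 12 weeks". It adds coefficients, marginal means and box plots by treatment group. There is no visit term.
- **Missing data.** SAP 8.6 plans descriptive summaries of the primary outcome over time by group. It starts from missing at random and leaves multiple imputation to the study statistician's discretion. The variables in the imputation model are not named.
- **Listed changes.** SAP 14 says in general terms that many protocol analyses are dropped because of the early end. It then itemises four secondary outcomes, the stratification factors, covariate adjustment, the cognition and depression subgroups, mediation and prediction modelling. The MLHFQ model is not in that list.
- **Pilot.** Protocol 2.2 reports on version 1 of the clinical worsening app against no app: "The App group had a reduced MLHFQ at 6 weeks (p=0.039) but not at 12 weeks (p=0.778) compared to control". On size it says only "Eighty-three patients were enrolled and completed all baseline assessments".

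**The concern.** A visit of the main patient-reported outcome is collected, the protocol named a method suited to it, and the SAP's replacement leaves it out of every effect estimate. A reader of SAP 14 would not learn that this method had been replaced.

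Two things are at stake. First, if either intervention helps soon after discharge and the benefit then wanes, the trial will hold the data to describe it but will have no planned estimate. Second, a participant who answered at week 6 and not at week 12 is left out of the regression unless imputation is used. The amendment history in protocol 10.4 gives low survey completion at both visits as the reason for widening the visit windows, so this group may not be empty, although no counts are given.

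**Working it through.** The documents give no MLHFQ effect size, SD or power, so there is no stated figure to reproduce. The check sets the passages side by side and then sizes what can be sized.

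**1. Where the week-6 MLHFQ enters the SAP**

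| SAP section | Week 6 used? | Treatment effect estimated? |
|---|---|---|
| 8.3 and 10.2, win ratio tier 3 | No, week-12 change | Yes |
| 9.2, derived variables | No, 12-week change | Not applicable |
| 10.3, regression | No, one change score each | Yes |
| 8.6, summaries over time | Possibly | No, descriptive |
| 8.6, imputation | Possibly, variables not named | Only by way of week 12, and discretionary |

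No row has both a stated use of week 6 and an effect estimate.

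**2. What the pilot p-values imply**

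Inputs: p=0.039 and p=0.778 (protocol 2.2). I assume 83 analysed at both visits, 1:1 allocation and a normal test. The numbers analysed are not given.

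- Week 6: |z| = 2.064, and d = |z| × sqrt(4/83) = 2.064 × 0.2195 = 0.45 SD.
- Week 12: |z| = 0.282, and d = 0.282 × 0.2195 = 0.06 SD, direction not stated.
- With only 60 analysed, the values are 0.53 and 0.07.

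**3. Illustration only: if that pattern recurred**

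The chance of a significant result in the favourable direction is Φ(d × sqrt(m/2) − 1.96), with m per group.

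- m = 225 (planned completers): week 6, Φ(4.81 − 1.96) = 0.998; week 12, Φ(0.66 − 1.96) = 0.096. With the 60-analysed values, the week-12 figure is about 0.12.
- m = 50 (assumed, since the final sample size is not given): week 6, Φ(2.27 − 1.96) = 0.62; week 12, Φ(0.31 − 1.96) = 0.05.

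A benefit of that shape would rarely show in a week-12 contrast. This describes one scenario and is not a forecast.

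**4. Does the pilot show fading?**

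That needs the correlation ρ between the two visits' estimates, which is not given. With equal numbers, equal SDs and the same direction, z for the difference is (2.064 − 0.282)/sqrt(2(1 − ρ)).

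- ρ = 0.4: 1.782/1.095 = 1.63.
- ρ = 0.8: 1.782/0.632 = 2.82.

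The answer runs from not significant to clearly significant, so the two p-values alone do not settle it.

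**5. What a two-visit model does to week 12**

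With complete data and free intervention-by-visit means, the week-12 contrast is the difference in mean week-12 change, the same as in SAP 10.3. With missing week 12, suppose a fraction r has week 6 only. In large samples the variance of the week-12 mean is then (1 − rρ²) times that from completers alone.

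Take r = 0.10, as if all of the plan's 10% dropout (25 of 250 per main arm) had a week-6 score:

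- ρ = 0.4: 1 − 0.10 × 0.16 = 0.984, a 1.6% reduction.
- ρ = 0.8: 1 − 0.10 × 0.64 = 0.936, a 6.4% reduction.

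The precision gain at week 12 is small. The main gains are the week-6 estimate and an analysis valid under the missing-at-random assumption that SAP 8.6 already makes.

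**6. Does the early end prevent it?**

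For each intervention the model needs four group-by-visit means and three covariance parameters, seven in all, fitted to data already collected.

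**The case against.** Much of the case on the other side stands, and it rules out several stronger readings.

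- **A reader might infer that an early benefit will be reported as no effect.** The documents do not support this. Week-12 change is the endpoint in both documents and week 6 is named as an endpoint in neither. A benefit that lasts would be seen, and one that has faded would correctly be reported as no difference at week 12.
- **A reader might infer that the SAP never touches week 6.** SAP 8.6 allows summaries over time and imputation, and either could draw on it. The tables and figures sit in a separate document not available here. What can be said is that the SAP text specifies no effect estimate at, or using, week 6.
- **A reader might take the pilot as showing the effect gone by week 12.** A p-value of 0.778 in about 83 patients is absence of evidence, and no effect sizes, intervals or week-12 direction are given. The pilot compared version 1 of the app with no app. Here the controls also have the app, the devices and the daily questionnaire. It says nothing about the dietary intervention.
- **A reader might cite protocol 4.3**, "HF patients are at greatest risk for hospital readmission and death for 7-weeks post-discharge and then the risk plateaus", as pointing to early quality-of-life effects. It concerns death and readmission, which the time-to-event tiers and Cox models cover.
- **A reader might suppose the protocol already prescribes visit-specific contrasts.** It names model classes only. A mixed model with a linear slope would comply and give no separate week-6 difference.
- **Secondary analyses are hypothesis-generating** (protocol 9.3.1), and simplification after an early stop is defensible. That limits the weight of the point. It does not explain why this change is left off the list, and a smaller trial makes setting aside a collected visit more costly.

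**Conclusion.** The point holds as a modest gap in analysis and documentation. SAP 10.3 drops the longitudinal approach that protocol 9.3.2 named for the MLHFQ, no treatment effect is estimated at or using week 6, and SAP 14 does not itemise the change. The trial could not describe an early effect from its planned analyses.

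The named week-12 result is barely affected: identical with complete data, and about 2% to 6% of variance if 10% have week 6 only and the correlation is 0.4 to 0.8, both assumed. The power figures (about 10% at week 12 against over 99% at week 6 with 225 per arm) hold only if the pilot pattern recurred with 83 analysed. They are a reason to look and should not be read as an expected effect. The primary win ratio is untouched. This is a cheap improvement, not a threat to the trial's main conclusion.

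**What to change.** - In SAP 10.3, for each intervention, fit a repeated-measures model of MLHFQ change at weeks 6 and 12 with intervention, visit and intervention-by-visit terms.
- Report the between-group difference with a 95% CI at each visit. Keep week 12 as the named secondary endpoint and label week 6 supportive and hypothesis-generating.
- In SAP 14, itemise the departure from protocol 9.3.2. If the simple regression is kept, list that change there and give the reason.
- Leave the primary win ratio on week 12.
- If the database is already locked when this is adopted, label the week-6 estimate post hoc.

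The cost is a few lines of SAP text and one standard model on data in hand. The downside is one extra supportive estimate per intervention, not adjusted for multiplicity.
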